9.3.1 Community-Enhanced Reach

We will conduct a series of community engagement activities in the intervention arms designed to reach persons at risk for HIV, undiagnosed with HIV or diagnosed and fallen out of care working closely with community health system, leveraging existing mobile outreaches in the community. The aim will be to reach all residents to offer health education, referral to study intervention components, and HIV and multi-disease screening. We will partner with ongoing MOH activities to leverage existing activities.

Community Engagement

The community engagement process will entail the multiple meetings with community leaders, health care leaders, members of the target population and other key stakeholders discuss the study and optimal approaches to community participation and mobilization, built on the approach used in the SEARCH study.

These meetings with key leaders and stakeholders will be held in each region to introduce the study, answer questions and engage members in advising on topics that include:

- Recruitment strategies
- Identification of potential challenges and solutions to implementation
- Optimum dates, times and locations of the activities
- Populations or communities that could require special consideration
- Other issues tailored to individual regions

In preparation for Community Mobilization activities, additional meetings with village leaders throughout each community will be held. Advertising for the events may include poster, leaflet and radio advertising, with the enlistment of community-based volunteers to describe the events and encourage participation. These efforts will incorporate the principles of a study community engagement plan which may include incentives at the Community Mobilization event, such as a raffle for prizes, supported by the community.

Community Mobilization Activities

Venues: Activity venues will be driven by existing health center outreaches and target populations. The number of venues and days in operation will be adapted to the needs of the individual participating communities. The venues will generally be open to receive participants during business hours, and may include evening or early morning hours as well to reach specific populations (such as fisherfolk, transport workers, or barmaids).

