Target Populations: Mobilization activities aim to engage adult men and women and adolescents living in each community who do not regularly access health care at local clinics, in order to provide health education and screening, and introduce health study interventions. Participants will meet with staff to review the services offered and provide informed verbal consent to take part. The verbal consent form will be read to them in the local language. Information will be collected from each community member, including name, village of residence, age, gender, and fingerprint biometric.

Pre-Test Counseling: After verbal consent, pre-test counseling will take place to describe to participants, in detail, the diagnostic services offered and answer questions. Education on the diseases for which community members are being screened will be provided, either in a group setting or on an individual basis.

Multi-Disease Screening: Multiple diagnostic services will be offered. HIV Antibody testing will be offered for all participants and additional measures and testing below may be offered and tailored to the population age and demographic.

- HIV testing will be performed according to country guidelines for those who do not self-report as HIV-positive according to country policy:
 - i. Initial rapid HIV test
 - ii. Participants with a negative result will be informed that they are HIV-negative
 - iii. Participants with an initial positive result will undergo a second rapid HIV test. If the result is positive, participants will be informed of their HIV-positive status.
 - iv. Participants with discordant rapid test results (first test positive, second test negative) will undergo a third “tie-breaker” HIV test. Participants with a positive “tie-breaker” test will be informed that they are HIV positive. Participants with a negative “tie-breaker” test will be informed that they are HIV-negative.
- Blood pressure: Blood pressure measurement for all ≥ 18 years
- Finger-stick blood random plasma glucose measure
- TB Screening: Symptom screening with referral to clinic for further evaluation via chest x-ray, sputum microscopy, and/or Xpert MTB/RIF assay^{64, 100}
- Malaria rapid diagnostic test (RDT) for participants with a temperature of $\geq 38^{\circ}\text{C}$

- STI testing, including syphilis and gonorrhea testing

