9.5. Phase B Measurements

Baseline and interim measures (Intervention only):

Through community-enhanced outreach, described above (Section 9.3.1), we aim to obtain baseline measures on all community residents (N=~80,000 persons; ~40,000 adults) in the intervention arm at the start of Phase B. Specific measures include multidisease screening (e.g., HIV, hypertension, TB) and corresponding care status. During the course of person-centered delivery, described above (Section 9.3.2), we will also collect and utilize data to improve intervention delivery. For example, providers will utilize life events assessment and plan (LEAP) forms to identify and address barriers to HIV viral suppression. Likewise, through the data-enhanced community precision health model, described above (Section 9.3.3), we will also use data collected in both the community and at clinics to inform targeted interventions for screening, linkage, and re-engagement. As detailed below (Section 9.6.2), we will also measure and assess intervention implementation.

There will be no study-specific measures prior to endline in control communities. We may obtain community-level data at baseline from existing MoH records.

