15.5 Community randomized trial in Phase B

In Phase B, we will randomize the $N=16$ study communities pair-matched on predictors of the primary endpoint (HIV incidence) and stratified by country.

We will assess population-level effects with Two-Stage TMLE, an approach appropriate for cluster randomized trials.^{5, 106} In Stage I, we estimate the outcome for each community. Then in Stage II, we use a cluster-level TMLE to estimate intervention effectiveness by comparing the community-specific endpoints between randomized arms. Given the limited number of clusters, we will use Adaptive Pre-specification to optimally adjust for covariate imbalance between randomized arms, while preserving Type-I error control.¹⁰⁸ In secondary analyses, we will implement the unadjusted estimator as the contrast of the arm-specific mean outcomes. For each endpoint, we will test the **null hypothesis** of *no improvement* from the intervention with a one-sided test at the 5% significance level. We will also report point estimates and two-sided 95% confidence intervals for each effect measure and the arm-specific mean outcomes.

The **primary study outcome** is HIV incidence among adult community members and assessed at month 30 with a recency assay. Stage I estimates of HIV incidence (per 100 person-years) will account for assay characteristics, such as mean duration of recent infection (MDRI) and false recent rate (FRR). Stage II estimates will use leave-one-out cross-validation to select from the following community-level covariates the combination that maximizes empirical efficiency: baseline HIV prevalence, baseline proportion with HIV who are suppressing viral suppression (<400 c/mL), or nothing (unadjusted).

The following secondary outcomes will be compared between arms using the analogous two-stage approach:

- **Biomedical prevention coverage:** proportion of HIV-negative follow-up time during which the participant was protected from HIV by PrEP or PEP (inclusive of CAB-LA)
- **Population-level viral suppression:** proportion of adults with HIV who are suppressing viral suppression (HIV RNA level < 400 c/mL) at month 30
- **Mortality:** the incidence (per 100 person-years) of death to illness and incidence of death due to all causes among adults
- **Annual incidence of active TB disease:** overall and stratified by age group and HIV-association
- **Hypertension control** (BP<140/90 mmHg) among community members aged 30+ years at month 30

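### Can Phase B adjust for baseline HIV prevalence and viral suppression when the study's own baseline data come only from the intervention arm?

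*Protocol*

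**What the plan says.** Protocol section 15.5 analyses Phase B in two stages. Stage I estimates HIV incidence in each community. Stage II compares the 16 estimates between arms with a cluster-level TMLE, using a one-sided 5% test. For the primary outcome, leave-one-out cross-validation picks the most efficient adjustment from "baseline HIV prevalence, baseline proportion with HIV who are suppressing viral suppression (<400 c/mL), or nothing (unadjusted". An unadjusted comparison is also planned as a secondary analysis.

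Section 9.5 describes the baseline data. Its subheading reads "Baseline and interim measures (Intervention only", and the text adds that "we aim to obtain baseline measures on all community residents (N=~80,000 persons; ~40,000 adults) in the intervention arm at the start of Phase B". For the other arm it says "There will be no study-specific measures prior to endline in control communities". The next sentence is "We may obtain community-level data at baseline from existing MoH records".

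Section 9.3.1 shows that the intervention-arm baseline comes from the intervention itself: "We will conduct a series of community engagement activities in the intervention arms". The outreach is meant to be broad ("The aim will be to reach all residents to offer health education"), and "HIV Antibody testing will be offered for all participants and additional measures and testing below may be offered". HIV RNA is not on its screening list.

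Sections 6 and 15.5 say that communities are pair-matched, the latter on predictors of HIV incidence. Neither names the predictors, and section 9.1.2 mentions only stratification by country. Section 15.5.1 states 80% power and cites covariate adjustment as one reason to think that figure conservative.

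**The concern.** A community-level covariate can be used in Stage II only if it is known for all 16 communities. Read together, sections 15.5 and 9.5 seem to leave two outcomes.

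- **The covariates do not exist in the control arm.** The adjustment cannot then be made, and the extra precision mentioned in section 15.5.1 is lost.
- **The two arms use different sources.** Intervention values would come from post-randomisation outreach and control values from MoH records. A systematic difference between the sources would act like a baseline imbalance that is not real, and adjusting for it would bias the primary estimate. Selecting covariates for efficiency does not detect this, and the unadjusted analysis that might reveal it is only secondary.

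The second outcome is the serious one, because it concerns the validity of the primary test.

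**Working it through.** **1. Does the text lead to either outcome?**

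- The MoH sentence in section 9.5 directly follows the sentence ruling out control-arm study measures. It refers to community-level data at baseline, which is the kind of covariate section 15.5 asks for. It is not limited to control communities, so one extraction covering all 16 is consistent with it.
- Pair-matching on predictors of incidence requires some common data on all 16 communities before arms are assigned. As the predictors are unnamed, this does not prove that prevalence or suppression is among them.
- Sections 9.3.3 and 9.5 give the intervention-arm data an operational use: targeting outreach, linkage and re-engagement. No section sends them to Stage II.
- With no HIV RNA in outreach screening, a suppression value would more naturally come from records in any case.

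**2. Does the stated power depend on the covariates?**

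Inputs from section 15.5.1: 8 communities per arm, 5,000 adults each, 90% tested, prevalence p = 0.10, incidence 0.5% against 0.3% (a 40% reduction), design effect 1.3, MDRI 238 (read as days), FRR 0.

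- Tested per arm: N = 8 × 5,000 × 0.9 = 36,000. MDRI in years: M = 238/365.25 = 0.6516.
- Proportion recent among HIV-positive adults: pR = I(1−p)M/p, giving 0.02932 (control) and 0.01759 (intervention).
- Expected recent infections: N·p·pR = 105.6 and 63.3.
- Delta-method variance of I = p·pR/((1−p)M): 1.3 × {[pR/((1−p)²M)]²·p(1−p)/N + [p/((1−p)M)]²·pR(1−pR)/(Np)}. This gives 3.09×10⁻⁷ and 1.85×10⁻⁷.
- SE of the difference = √(4.94×10⁻⁷) = 0.000703, and z = 0.002/0.000703 = 2.846.
- Two-sided 5%: Φ(2.846 − 1.960) = 81.2%, against 80% stated.
- One-sided 5%, as in the analysis: Φ(2.846 − 1.645) = 88.5%.

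No covariate enters. The MDRI's own uncertainty is not given. If it is assumed to be shared by both arms with a relative SE of 5% or 10%, two-sided power is 80.4% or 78.1%.

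**3. What if the covariates are unavailable?**

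Expected recent infections per control community are 5,000 × 0.9 × 0.9 × 0.005 × 0.6516 = 13.2. A design effect of 1.3 then implies a between-community incidence CV of √(0.3/13.2) = 0.151. A simulation used 6,000 replicates per scenario, 16 communities in two countries, lognormal prevalence (mean 10%, assumed CV 0.30) and Poisson recent infections. It applied linear adjustment or none by leave-one-out error, matches broken, and a one-sided 5% t test. With a true 40% reduction, power at assumed prevalence–incidence correlations r = 1.0/0.8/0.5/0.3 is 92/91/89/88% with the covariate available and 88–89% without it. The loss is 3.6/2.2/1.0/0.5 points.

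**4. What if sources did differ by arm?**

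One-sided rejection with no true effect, from the same simulation:

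| Control prevalence recorded | r=1.0 | 0.8 | 0.5 | 0.3 | 0 |
|---|---|---|---|---|---|
| Same source | 4.7% | 4.6% | 4.8% | 4.9% | 5.7% |
| 10% too low | 10.0% | 6.8% | 6.7% | 6.2% | 5.8% |
| 20% too low | 17.1% | 12.5% | 8.6% | 7.6% | 5.5% |
| 20% too high | 2.0% | 2.8% | 4.3% | 4.5% | 5.6% |

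With a true 40% reduction and 20% over-recording, power is 80/81/84/85% at r = 1.0/0.8/0.5/0.3. In a repeat of the 20% under-recording case with 4,000 replicates, keeping the pairs lowered the r = 1.0 figure from 16.6% to 11.5%. At r = 0.5 and 0.3 the procedure chose no adjustment in about 67% and 77% of runs. The mis-recording, r and the prevalence CV are all assumptions. A linear model stands in for the TMLE, and suppression was not simulated.

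**The case for a change.** The best case for a change is that permission to obtain MoH data is not a commitment. The sentence sits beside the statement about control communities, and nothing forbids using outreach data for the intervention arm. The consequences are also lopsided: dropping a covariate costs at most about 4 points of power, whereas a strongly prognostic covariate measured differently by arm could double or triple the type I error. Offering no adjustment as a candidate does not remove that risk, because selection looks only at efficiency. A sentence or two would close the gap.

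Two parts of this stand. The source of the two covariates is not named, and a common source, definition and period in all 16 communities is a condition for valid adjustment. What does not stand is the step from an unnamed source to a flawed primary test. To reach it, analysts would have to choose, without any instruction, a post-randomisation source in one arm and a different source in the other. Section 15 describes itself as an overview. The SAPs at hand cover the Phase A trials, where candidate covariates are set out trial by trial, so a Phase B SAP is the natural place for this detail.

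**Conclusion.** No change to the plan is needed. Sections 9.5 and 15.5 leave the source of two optional covariates unstated, but they do not contradict each other. MoH data for all 16 communities are allowed, and an analyst preparing a community-level adjustment would be expected to use one source for both arms. If a covariate cannot be obtained that way, the option of no adjustment already applies. The cost is then 0.5 to 3.6 points of power at the assumed correlations of 0.3 to 1.0. The stated 80% does not rely on adjustment (81.2% recomputed), and the planned one-sided test alone brings the figure to 88.5%.

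The type I error figures of up to 17.1% show only why a common source matters. They depend on an arm-specific sourcing choice that appears nowhere in the documents, and on values for mis-recording, correlation and prevalence spread that the documents do not supply. This conclusion assumes that outreach data are not used for adjustment in Stage II. Evidence that they were would reopen the question.

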15.5.1 Power calculations for Phase B

For primary endpoints of HIV incidence, we present the following power calculations based on *inctools R* package,¹ which implements and extends the HIV incidence methods of Kassanjee et al.¹¹² The *R* package is a more robust implementation of the prior ABIE (Assay Based Incidence Estimation) spreadsheet tool, developed by the CEPHIA (Consortium for the Evaluation and Performance of HIV Incidence Assays). When possible, we used prior data to inform key parameters, including (i)community size, (ii) HIV prevalence, (iii) expected testing coverage, (iv) expected outcome under the standard-of-care, and (v) recency assay characteristics.^{2,3} We expect these calculations to be conservative, because of the precision gained through our pre-specified choice of a one-sided hypothesis test and through covariate adjustment during the analysis.^{5, 104, 106}

With 16 communities (8 per arm) each with ~5000 adults, 10% HIV prevalence, and 90% testing coverage, we anticipate being powered at 80% to detect a 40% relative reduction in annual HIV incidence from 0.5% in the standard-of-care (control) with a two-sided hypothesis test ($\alpha=0.05$), a design effect of 1.3, mean duration of recent infection (MDRI) of 238, and false recent rate (FRR) of 0%. As shown in **Figure 6**, these calculations are fairly robust to the test coverage achieved and HIV incidence under the standard-of-care.

[figure not shown]

Figure 6: For the Phase B cluster randomized trial, the effect size (in relative reduction in HIV incidence) detected with 80% power varying testing coverage and HIV incidence under the standard-of-care (control).

15.6 Additional explanatory and descriptive analyses for Phase B

For the 16 communities participating in Phase B, we will provide descriptive statistics of the baseline characteristics of study participants, overall and stratified by country. Characteristics reported will include sex, age, marital status (single, married, widowed, divorced/separated), education (no school, primary, secondary, post-secondary), occupation, and mobility. For each study outcome compared between arms, we will also report formal consort diagrams as well as participant flow diagrams enumerating inclusions and exclusions for all clusters and individuals contributing to each analysis.

Implementation evaluation will be based on the RE-AIM framework. We will also conduct multivariable analyses to evaluate risk factors for poor outcomes, including viral non-suppression, low prevention coverage among persons at risk of HIV, and HIV seroconversion. Variable importance measures will be estimated with a pooled individual-level TMLE with the community

treated as the independent unit.¹⁰⁶ We will implement analogous predictor analyses for other community health outcomes.

To inform our understanding of mechanisms of action, we may specify hierarchical causal models to represent the relationships between key study variables, including the community-level intervention, community-level mediators, individual-level mediators, and individual-level outcomes.^{104, 109, 110} We may assess mediation at the community-level, using methods analogous to the individual-level mediation analyses. We may augment these cluster-level analyses with multi-level mediation analyses.

16. PUBLICATION POLICY

The findings from this study may be published in a medical journal. No individual identities will be used in any reports or publications resulting from the study. The researchers will publish results of the study in accordance with NIH, UCSF, UNCST, KEMRI and Makerere University guidelines.

This Appendix describes the continuation of the 3 Dynamic Prevention Randomized studies (refer to section 9.2.1 of protocol) for a 48 week follow up period following re-consent for this CAB-LA extension. Persons who are already enrolled in the trials and were randomized to the intervention arm will be eligible to receive CAB-LA as one of the options in the “Dynamic prevention” model. Persons in the control arms will be eligible to receive CAB-LA if and when it is rolled out through in country programs. If CAB-LA is not available in country at the 48-week endpoint, all participants in the intervention arm will have the opportunity to continue in the study until Week 96, and participants who are currently on CAB-LA may continue through the extension. The study will end at Week 96, and by that time participants will be transitioned to in country prevention care. At 96 weeks, persons on CAB-LA will be transitioned to in country CAB-LA or to other prevention options if CAB-LA is not available. Prior to this transition, available in country options will be assessed by the study team. HIV prevention options will be discussed with each study participant by their Week 88 visit, with a plan established for the transition to the participant’s preferred prevention method in coordination with local health facilities to avoid interruption after their 96 weeks of study participation is completed.

The overall purpose of this extension is to 1) Determine if adding the option of CAB-LA as a prevention choice using a patient-centered HIV prevention delivery model increases prevention coverage (i.e. proportion of time that is covered by a biomedical prevention option, such as PrEP or PEP) compared to the standard-of-care in 3 ongoing randomized trials of Dynamic Choice Prevention in rural Uganda and Kenya; and, 2) Conduct a hybrid implementation study (Primary Objective Clinical and Secondary Objective Implementation) focusing on initial implementation of a patient-centered model for CAB-LA using the RE-AIM evaluation framework among persons randomized to the intervention arms.

A. Background and Rationale

Background: SEARCH Sapphire is an ongoing, NIH-funded study that is testing multi-disease and multi-sector interventions aimed at reducing HIV burden and improving health in rural Uganda and Kenya. Phase A is a portfolio of randomized prevention and treatment implementation studies that will inform a population-level study in Phase B (refer to section 3.0 of protocol).

This appendix describes a 48-week extension of 3 ongoing randomized trials in Phase A studying a patient-centered “Dynamic Choice Prevention” (DCP) implementation strategy for delivering existing evidence-based biomedical prevention interventions vs. standard of care (SOC). The Dynamic prevention model offers participants choices on prevention modality on an ongoing basis: oral PrEP, or oral PEP, and the option to switch between products. The trials are being conducted in 3 settings: antenatal (ANC) clinics, the outpatient department (primary care clinics), and in rural community settings in Western Kenya and Uganda (refer to section 9.2.1 of protocol). All clinic and village health team staff (i.e., Clinical Officers, nurses, coordinators, health workers) are trained and equipped for HIV prevention care in the clinical setting, appropriate to their role (refer to section 9.2.1.1 of the protocol).

In the CAB-LA extension, participants in the intervention and control arms are reconsented and remain in their initial randomized arm. Persons in the intervention arms who remain HIV

negative will be offered CAB-LA as an additional biomedical prevention option, if eligible. CAB-LA will be delivered at health clinics. The primary 48-week endpoint for this extension is proportion of time covered by a biomedical prevention product. As of May 9, 2022, a total of 1213 HIV-negative persons aged 15 years and older and at risk for HIV acquisition were enrolled in the studies. (Table 1). New participants are being enrolled at the present to time to replace those participants who have moved and have been unable to continue in the CAB-LA study. The total number of participants in the study eligible for CAB-LA will not exceed the 593 listed in Table 1.

Table 1. Enrollment in 3 SEARCH Sapphire Dynamic Prevention Trials as of May 9, 2022

Dynamic Prevention Study	Intervention and Control, (N) Uganda	Intervention (N) Uganda	Intervention and Control, (N) Kenya	Intervention (N) Kenya	Total Enrolled (N), Intervention and Control	Total Enrolled Intervention (N)
Antenatal/SRH Clinic	200	100	201	103	401	203
Outpatient Department Clinics	201	100	201	97	402	197
Household Study Community Village Health Team (VHT)	200	83	210	110	410	193
All Trials Together	601	283	612	310	1213	593

Population: The persons eligible for participation in the extension are those who were enrolled in the 3 ongoing trials. Persons for the ANC study are recruited and enrolled through offering study participation at ANC clinics at government sponsored health facilities. Persons for the Outpatient department are recruited and enrolled through offering study participation at Outpatient department clinics at government sponsored health facilities. Persons for the community study are recruited via home visits by village health teams/community health workers (refer to section 7.5.1 of protocol).

Inclusion criteria for the Extension include:

- 1) Enrollment in a SEARCH Sapphire Dynamic prevention study
- 2) HIV negative at start of extension
- 3) Residing in study region

Additional inclusion criteria to access CAB-LA as a prevention option

- 1) Not pregnant at time of initial CAB-LA injection
- 2) Participant weighs at least 35kg

Additional Exclusion Criteria to access CAB-LA as a prevention option

- 1) Participant has Hepatitis B or chronic Hepatitis C Diagnosis
- 2) Participant has ALT ≥ 5 ULN
- 3) Participant has clinical history of liver cirrhosis or current clinical evidence of cirrhosis or severe liver disease
- 4) Previous hypersensitivity reaction to cabotegravir

- 5) Receiving the following co-administered drugs for which significant decreases in cabotegravir plasma concentrations may occur due to uridine diphosphate glucuronosyltransferase:
 - i. Anticonvulsants: Carbamazepine, oxcarbazepine, phenobarbital, phenytoin
 - ii. Antimycobacterials: Rifampin, rifapentine
- 6) Participants with a current or anticipated need for chronic systemic anticoagulation or a history of known or suspected bleeding disorder, including a history of prolonged bleeding, except for the use of anticoagulation for deep vein thrombosis (DVT) prophylaxis (e.g., postoperative DVT prophylaxis) or the use of low dose acetylsalicylic acid (≤ 325 mg).

Study Intervention Clinic Locations: All participating ANC and OPD clinics in the DCP trial will offer CAB-LA. For VHT/CHV communities, the nearest health facility will offer CAB-LA for all participants

- 1) In Uganda, the sites for each of the trials:
 - a. OPD: Itojo Hospital, Kitagata Hospital
 - b. ANC: Bwizibwera HCIV, Bushenyi HCIV
 - c. VHT: Ndeija Health Center III
- 2) In Kenya, the sites for each of the trials:
 - a. OPD: Magunga Level IV Hospital, Oyani Hospital
 - b. ANC: Oyani Hospital, Sena Health Centre
 - c. CHV: Sibouche Health Centre, Ogongo Sub-District Hospital

The demographic characteristics of the persons enrolled in the intervention arm as of May 9, 2022 currently who will be eligible for CAB-LA patient-centered intervention are shown in Table 2.

Table 2. Demographics of persons in intervention arm eligible for CAB-LA in extension phase of trial as of May 9, 2022.

	ANC Clinic	Outpatient Department	Community
Total Enrolled	203	197	193
Female Participants	203 (100%)	119 (60.4%)	111 (57.2%)
Age years number and %			
15-25 years	120 (56.9%)	90 (44.1%)	75 (38.9%)
26- 30	47 (22.3%)	33 (25.0%)	29 (25.4%)
31-40	35 (16.6%)	51 (16.2%)	49 (18.7%)
41-60	9 (4.3%)	26 (12.7%)	36 (15.0%)
61+	0 (0%)	4 (2.0%)	4 (2.1%)

Rationale: HIV prevention services that offer choice of prevention products (PrEP & PEP) and flexibility in their use and location of delivery over time allow for a dynamic, patient-centered model of prevention. This approach is responsive to the reality of an individual's changing needs, thereby facilitating continued engagement. CAB-LA is highly efficacious for HIV prevention that was recently approved by the US FDA based on two large, randomized trials HPTN 083 and HPTN 084. As CAB-LA is rolled out across rural sub-Saharan Africa, it is

important to determine **how the addition of this option impacts prevention coverage in real-world settings** for women and men at risk for HIV. In addition, it is critical to design, evaluate, and improve **patient-centered CAB-LA delivery** strategies that maximize uptake and impact of this new product.

Ethical Considerations: The HPTN 084 study that showed efficacy of CAB LA for prevention included sites in both Uganda and Kenya. Applications for approval of CAB LA are under review in each of these countries. Thus, the information generated in this study on evaluating a dynamic prevention implementation strategy will be directly applicable. *During this proposed study extension, CAB LA is expected to become publicly available through Ministry of Health ("MoH") sponsored programs (in both Kenya and Uganda). UCSF is developing an additional extension to 96 weeks, which will examine longer-term safety and implementation data of CAB-LA. Should there be delay in rollout of the MoH programs, participants could continue in this additional extension phase. After the endpoint of the 96-week extension is reached, participants will be transitioned to a standard of care regimen, via local healthcare system, based on the investigator's clinical judgment and local country guidelines*

B. Hypothesis and Objectives

Hypotheses: A dynamic choice prevention model that includes a patient-entered CAB-LA delivery option will have higher levels of biomedical prevention coverage (assessed over 48 weeks following re-consent for the CAB-LA extension study) compared to the standard of care.

This hypothesis will be tested by comparing covered time between the intervention and control arms in the 3 ongoing randomized trials during the extension phase.

The secondary hypothesis: Addition of patient-centered CAB-LA into an ongoing dynamic choice prevention will improve biomedical prevention coverage (compared to dynamic choice prevention without CAB-LA).

These hypotheses will be tested by comparing covered time during the extension with the CAB-LA option to covered time prior to the extension among intervention arm participants.

We expect that incorporating the option of CAB-LA with patient-centered delivery for persons who self-identify at risk for HIV living in rural Uganda and Kenya will increase overall biomedical covered prevention time compared to the standard of care. In a population that has been offered -- and some of whom have taken up -- oral PrEP and PEP, we also expect to learn characteristics of who is most interested in CAB-LA, how our patient-centered CAB-LA delivery models work in different settings, and the cost of the delivery models in different settings.

Primary Objective: To compare biomedical prevention coverage achieved using a Dynamic prevention model that includes a patient-centered CAB-LA delivery intervention to biomedical prevention coverage under the standard of care over 48 weeks.

[figure not shown]
Secondary Objectives: To determine the reach, effectiveness, adoption, implementation and maintenance of a patient-centered CAB-LA program embedded in 3 ongoing trials in the setting of antenatal clinic, outpatient clinic, and community.

Tertiary Objectives: To evaluate change in knowledge, awareness and acceptability/satisfaction at the staff and provider level with CAB-LA before and after provider and staff training and education in CAB-LA with patient-centered delivery model.

C. Study Design and Schema

Study Design: This proposal is an **extension of 3 ongoing randomized trials comparing a patient-centered “Dynamic Choice” implementation strategy for delivering biomedical prevention options compared to standard of care** (Figure 1). Each trial is enrolling persons 15 years of age and older who are HIV uninfected and at risk of acquiring HIV. The Dynamic Choice Prevention intervention allows choice of PEP/PrEP, refill schedule, service delivery location (e.g. clinic, community, home), and HIV testing (self or staff). Persons can move from PEP to PrEP as they prefer (refer to section 9.2.1.4 of protocol).

Figure 1. Dynamic Choice Implementation Strategy

Intervention: In the extension phase, participants will remain in their initial randomization arm. For persons in the intervention arm, CAB-LA will be integrated into the dynamic choice delivery model as an additional biomedical prevention option in a patient-centered delivery model based on the precede framework.

The Dynamic Choice Delivery Model includes integrated PrEP and PEP services at outpatient clinics, antenatal clinics, and via VHT workers in community households. The procedures for each trial include PrEP/PEP counseling and services, choice of service location, HIV testing options, option for longer PrEP refills, provision of a clinical officer’s or nurse’s mobile telephone number for immediate PEP starts any day of the week, assessment of PrEP/PEP barriers and personalized actions, psychologic supports for traumatic experiences, and offer of concurrent, additional health or prevention related services (Table 10 of Main Protocol). For participants that chose CAB-LA as the biomedical prevention option, the patient-centered delivery model (Table 3) will be implemented. The standard of care differs according to country but does not routinely offer PEP or PrEP to clients seeking services, does not offer choice of service location, HIV testing option or access to medical provider mobile phone number. Clients are required to return

after one month for a refill for PREP, whereas in our model, there is an option from the start for 3 month medication supply.

Table 3. Patient-Centered Delivery Model

Intervention	Population and frequency	Purpose
Education, case studies and discussion on concept of dynamic prevention and on the profile of each prevention option product	Health center leadership and staff, provider, participants; initial and ongoing	Predisposing
Integration into antenatal, OPD clinics, IPV/GBV support services, travel packs, 24 hour hotline for participants For oral PrEP/PEP only- HIV testing choice (self or staff) and home or clinic delivery	Participants; ongoing	Enabling
Provider text/check-in to participant one week after starting new option, data on biomedical prevention covered time (reinforcing)	Participants and staff; ongoing data feedback	Reinforcing

Outcomes: The primary outcome for the extension is the proportion of time covered by a biomedical prevention option during the 48 week follow-up period of the CAB-LA Extension; follow-up time will be censored at HIV diagnosis, death, or withdrawal. Biomedical covered time is defined as the proportion of follow-up time that each participant is covered by either PrEP (TDF/3TC or CAB-LA) or PEP. For TDF/3TC, covered time is defined using self-reported use; in a subset of participants who report PrEP use we will measure tenofovir drug levels using small hair samples to allow for calibration of self-reported measures. For CAB-LA, coverage begins 3 days after initial injection and continues 2 months + 7 days after last injection. For PEP, covered time is defined using self-reported use; in a subset of participants who report PEP use we will measure drug levels using hair samples to allow for calibration of self-reported measures. A secondary outcome for the extension is “at-risk covered time”, defined as the proportion of time that a participant reports being at risk of HIV infection during which they are covered by a biomedical prevention option. Incident HIV infections, defined by a prespecified testing algorithm, will be an additional secondary outcome.

Secondary outcomes of reach, effectiveness, adoption, implementation and maintenance will be evaluated using a mixed methods approach that includes surveys of participants, and health center providers and staff. Tertiary outcomes of knowledge, awareness and acceptability/satisfaction at the staff and provider level will be measured by surveys at the baseline, midpoint and end of the study. Measurement details delineated in Table 4 .

In addition to these surveys, trained staff will conduct in depth interviews (IDI) to provide insights into the intervention implementation and attitudes of participants and staff. These qualitative in-depth interviews will be conducted among purposively-selected samples of study participants and providers, to ascertain the perceptions of and experiences with CAB-LA use and delivery. Participants who are clients will be asked about 1) Experiences with counseling, method/service preferences and decision-making to go on CAB-LA; 2) Method/services satisfaction, barriers and facilitators to uptake and maintenance, and social networks and support as a facilitator or hindrance; and 3) Recommendations to improve CAB-LA Delivery. Health care providers engaged in CAB-LA service delivery will be asked about their 1) Professional identity and motivation, as a potential factor influencing implementation; 2) First impressions and knowledge

of CAB-LA; 3) Clinical training experiences relevant to CAB-LA provision; 4) Experiences with and acceptability of individual elements of CAB-LA; and 5) Recommendations for improving CAB-LA delivery.

For all research activities related to qualitative evaluation of SEARCH SAPPHIRE, written informed consent will be obtained from all selected for recruitment to the study.

Qualitative IDIs for CAB-LA will be conducted between 2-6 months from enrolment. The specific data collection activities to be conducted during the phase are listed below. For Seroconverts, IDIs are will continue until the maximum number of participants is reached or the study intervention ends, whichever comes first.

- i. CAB-LA Patient IDI cohort: We will systematically select $\sim n=30$ patients per each region (South West Uganda and Kenya) (total $40 < \sim n < 72$), with samples within region to be balanced by original trials (Out- patient, ANC/PNC, VHT); further balance to be observed by gender and community, proportional to overall intervention enrolment.
- ii. CAB-LA Provider IDI cohort: We will select a sample of care providers who administer CAB-LA from the CAB-LA trial health facilities or who inform the community about that option (VHTs / CHVs per each region. I.e. $n=2-3$ OPD providers, $n=2-3$ ANC/PNC providers, $n=1-2$ VHTs per region (total $8 < \sim n < 12$ providers per region).
